- (1) NR-treatment will reduce capsaicin-induced axonal degeneration in the epidermis in healthy controls.
- (2) NR-treatment will enhance axonal regeneration after capsaicin-induced epidermal denervation in healthy controls.

3. Background

Small fiber neuropathy (SFN) manifests in a variety of different diseases and often results in symptoms of burning pain, shooting pain, allodynia, and hyperesthesia (Tavee and Zhou, 2009). Although strength remains preserved in patients with SFN, the pain and paresthesia's are often disabling. Diabetes mellitus (DM) and impaired glucose tolerance (IGT) in combination with metabolic disease are the most common identified causes of SFN (Hovaguimian and Gibbons, 2011). In these cases, besides strict glucose control, no other treatment option has demonstrated the ability to slow or prevent axon loss in people with diabetic patients with peripheral neuropathy.

Pathologically, the peripheral nerve damage in patients with SFN affects predominantly or exclusively the small myelinated (A δ) fibers or unmyelinated C fibers. Many small fiber neuropathy patients test normally on conventional electrophysiological tests because intraepidermal nerve fiber function is not assessed by routine nerve conduction studies. Thus, in many patients, the only objective evidence of neuropathy is by skin biopsy determining the intraepidermal nerve fiber density (IENFD) in the collected skin tissue samples (Holland et al., 1998),

The capsaicin cream is an FDA approved medication available over the counter for treatment of various conditions including arthritis related joint pain and post herpetic neuralgia (Fernandes et al., 2016). It is the active ingredient in hot chili peppers and has been shown to bind vanilloid receptors on C- and A-delta nerve fibers leading to calcium entry and subsequent axonal degeneration (Marsh et al., 1987; Pini et al., 1990). The application of over-the-counter strength capsaicin cream (0.1%) for 48 hours leads to loss of intraepidermal nerve fibers mimicking the changes seen in small fiber neuropathies (Simone et al., 1998; Nolano et al., 1999). Associated with the loss of intraepidermal nerve fibers is a decrease in sensation in the area of the patch. Over weeks to months, the fibers slowly regenerate, repopulating the treated area ([name] et al., 2004; Hahn et al., 2007). This regenerative response is associated with improved sensory function as well.

[figure not shown]

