Nicotinamide riboside (NR) is a pyridine-nucleoside form of vitamin B3 that functions as a precursor to nicotinamide adenine dinucleotide or NAD⁺. Studies in mice have shown that boosting the levels of NAD⁺ can produce multiple health benefits, including reducing nerve damage (Trammell et al., 2016a; Hamity et al., 2017). In humans, the levels of NAD⁺ diminish with age and it has been suggested that loss of this metabolite may play a role in age-related health decline (Johnson and Imai, 2018). NR is FDA approved as a dietary supplement and can be purchased over the counter.

4. Study Procedures

a. Study design:

This is a randomized double-blinded study to evaluate the effects of NR on experimental axon degeneration and regeneration. After the initial screening (visit 1) is completed, the patients will undergo a skin biopsy and be randomized to either the study drug or placebo and will be instructed to take it for a week prior to visit 2. Based on existing pharmacokinetic studies, this should be sufficient to raise the plasma NAD levels at the time of experimental denervation of the skin. At visit 2, patients will undergo two baseline skin biopsies and application of the capsaicin patch for 48 hours and will be instructed to continue the study drug. At visit 3 (48 hours after visit 2), capsaicin patch will be removed, and a repeat skin biopsy will be done to evaluate the degree of epidermal denervation. Patients will be instructed to continue the study drug for another 3 months and will undergo repeat skin biopsies at 2 months (visit 4) and 3

months (visit 5). Blood samples will also be drawn at each visit to measure NAD levels to confirm compliance and to correlate with degree of epidermal innervation. Figure 1 depicts a schema of visits and timelines.

b. *Study duration and number of study visits required of research participants.*

As outlined above, there will be a total of 5 visits over 3 and ½ months.

c. *Blinding, including justification for blinding or not blinding the trial, if applicable.*

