Not applicable

7. Study Statistics

- a. *Primary outcome variable.*

We are testing whether NR will reduce axonal degeneration as well as promote regeneration. The primary outcome will be the measurement of epidermal nerve fiber counts.

- b. *Secondary outcome variables.*

Plasma NAD levels will be measured and correlated with primary outcome measure

- c. *Statistical plan including sample size justification and interim data analysis.*

Aim 1 focuses on the ability of NR to reduce or prevent nerve fiber degeneration in the capsaicin model. From past studies, we know that following topical capsaicin application, the epidermis is nearly completely denervated. A previous study of 66 healthy control subjects, the baseline intraepidermal nerve fiber density was 22.7 ± 10.1 fibers/mm ([name] et al., 2006). Following 2 days of topical capsaicin application, the post-capsaicin IENFD was 0.25 ± 0.04 fibers/mm (nearly 99% reduction in nerve fiber density).

We expect a very similar study subject profile in the current study. If that is true, 20 subjects/arm will have a power of 0.8 to detect a difference in post-capsaicin epidermal nerve fiber density between NR and placebo of as low as 0.035 fibers/mm. If our subjects show more variability (standard deviation of 0.06 instead of 0.04) we would still have a power of 80% to detect a difference of 0.055 fibers/mm. Therefore, we are confident that a sample of 20 subjects/group is sufficient to determine whether NR decreases axonal degeneration in our model.

Aim 2 focuses on the potential for NR to promote IENFD regrowth. Following denervation with topical capsaicin, epidermal nerve fibers re-innervate the epidermis in a predictable fashion. Biopsies taken at two and three months following denervation have higher IENFD, the rate of regrowth is determined by calculating the slope of the line of IEND against time. Across several studies, this rate of nerve fiber regrowth has been 0.18 ± 0.08 fibers/mm/day ([name] et al., 2004). A sample of 20 subjects/group will have a power of 0.8 to detect a 40% or greater change in nerve fiber regeneration. We will have a power of 0.6 to detect a 30% improvement in regeneration.

- d. *Early stopping rules.*

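### Aim 1 compares only the fibre density left after capsaicin and states no use of the pre-drug biopsy already taken; adjusting for it could recover precision at almost no cost

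*Combined protocol and SAP*

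**What the plan says.** Section 2 states hypothesis 1 as "NR-treatment will reduce capsaicin-induced axonal degeneration in the epidermis in healthy controls". Section 7a adds only that "The primary outcome will be the measurement of epidermal nerve fiber counts", with no time point, change score, ratio or covariate.

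The Aim 1 paragraphs of section 7c are the only place where a between-arm comparison for this hypothesis is described, and they do so through the sample size: 20 per arm are given a power of 0.8 to "detect a difference in post-capsaicin epidermal nerve fiber density between NR and placebo of as low as 0.035 fibers/mm". The inputs are that "the post-capsaicin IENFD was 0.25 ± 0.04 fibers/mm" and, as a less favourable case, a "standard deviation of 0.06 instead of 0.04". The same section reports that "the baseline intraepidermal nerve fiber density was 22.7 ± 10.1 fibers/mm", but uses that figure only to show that nearly all fibres are lost. No test or model is named.

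Section 4a sets out the biopsies. After screening at visit 1, "the patients will undergo a skin biopsy and be randomized to either the study drug or placebo". Study drug is then taken for a week. Two further biopsies, which the protocol also calls baseline, come at visit 2 just before capsaicin, and the post-capsaicin biopsy at visit 3, 48 hours later. No role in the Aim 1 analysis is stated for the visit-1 or visit-2 biopsies.

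**The concern.** Degeneration is a loss from a person's own starting point. Residual density measures that loss directly only if everyone starts from much the same level, and by the plan's own figures they do not: the coefficient of variation at baseline is 10.1/22.7 = 44%. Two people at 33 and 13 fibers/mm, roughly one SD either side of the mean, can finish with the same residual density after different proportional losses.

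To the extent that residual density tracks starting density, the unadjusted comparison carries variation that the trial has already measured and could remove. What is at stake is power for Aim 1.

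A second consequence follows from section 4c, under which the principal investigator carries out the analysis after the code is broken. With no model named, the choice between raw, changed, proportional or adjusted density, and between visit 1 and visit 2 as baseline, is still open at that point.

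**Working it through.** **Inputs.** From section 7c: 20 per arm; post-capsaicin mean 0.25 and SD 0.04 (alternative 0.06); detectable difference 0.035 (alternative 0.055); baseline 22.7, SD 10.1 fibers/mm. Assumed because the documents give neither: two-sided 5% significance, and the correlation r between visit-1 and visit-3 density, shown over a range. No dropout is applied.

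**1. The plan's own figure.** The SE of the arm difference is SD × sqrt(2/20).
- SD 0.04: SE = 0.0126; 0.035/0.0126 = 2.77. Power is 0.79 by the normal approximation and 0.77 by the t-test (38 df).
- SD 0.06: SE = 0.0190; 0.055/0.0190 = 2.90. Power is 0.83 (normal) and 0.81 (t-test).

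The stated 80% is therefore reproduced, to rounding, by an unadjusted two-sample comparison of residual density. A one-sided 5% test gives 0.87 for the first case and does not fit.

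**2. Effect of adjusting for visit-1 density.** The residual SD becomes 0.04 × sqrt(1 − r²). The test has 37 df, and the variance is inflated by 1 + 1/36 to allow for chance imbalance in the covariate. Power for 0.035:

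| r | Residual SD | Power |
|---|---|---|
| unadjusted | 0.0400 | 0.77 |
| 0 | 0.0400 | 0.76 |
| 0.3 | 0.0382 | 0.80 |
| 0.5 | 0.0346 | 0.87 |

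**3. How far a baseline imbalance can move the endpoint.** The SE of the arm difference in baseline mean is 10.1 × sqrt(2/20) = 3.19 fibers/mm. The slope of residual on starting density that the stated SDs allow is r × SD/10.1, so a one-SE imbalance moves the endpoint by r × SD × sqrt(2/20).
- SD 0.04: 0.0126 at r = 1; 0.006 at r = 0.5; 0.004 at r = 0.3.
- SD 0.06: 0.019 at r = 1.

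At SD 0.04 and r = 1, a shift of 0.035 needs an imbalance of 0.035 × 10.1/0.04 = 8.8 fibers/mm. That is 8.8/3.19 = 2.77 SE, with two-sided probability about 0.006.

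**4. Type I error.** In simulations of the unadjusted t-test with no treatment effect, the rejection rate was 0.050 to 0.052 for r of 0, 0.5 and 0.9.

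**5. Simple change from baseline as an alternative.** Its SD is sqrt(10.1² + 0.04² − 2r × 10.1 × 0.04), which is about 10.1 at any r. The difference detectable with 80% power is then about 9.2 fibers/mm, so a raw change score would swamp the endpoint.

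**The case against.** The passage in 7c is a sample-size statement, not an analysis plan. It cannot be read as a decision to leave baseline out; the fair description is that no use of it is stated. That stands, and the wider gap is that no Aim 1 model is given at all.

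Randomisation already puts chance imbalance inside the standard error of the unadjusted comparison, and the simulated type I error confirms it. That stands too. A reader might infer that imbalance could pass for protection and invalidate the result, but the documents do not support this.

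A reader might also infer that an ordinary imbalance could move the endpoint by the whole 0.035. If everyone kept the same 0.25/22.7 = 1.1% of fibres, a one-SE imbalance would indeed give 3.19 × 0.011 = 0.035. But that model forces a post-capsaicin SD of at least 0.011 × 10.1 = 0.111, which is 2.8 times the 0.04 behind the 0.035 and 1.9 times the 0.06. Coefficients of variation of 44% before capsaicin and 16% (0.04/0.25) after it do not fit full proportionality. If the SD really were 0.111, unadjusted power for 0.035 would be about 0.16 to 0.17, and the main fault would lie in the SD rather than in the missing covariate.

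Finally, a linear model with a baseline covariate estimates an adjusted difference in residual density, not a proportional loss. That is correct. The adjustment brings the comparison closer to hypothesis 1 without turning it into a percentage-loss analysis.

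**Conclusion.** The point holds as one of precision and specification. Section 7c states no use of a pre-drug measurement that the trial already collects, for a hypothesis about loss and in a population whose starting density varies by 44%.

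On the plan's SD of 0.04, adjustment changes power for 0.035 from 0.77 to between 0.76 and 0.87 over correlations from 0 to 0.5. The correlation is an assumption, so the gain cannot be stated more narrowly; the loss if there is none is about 1 point. The unadjusted test remains valid and unbiased.

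These figures also assume a two-sided 5% level and that 0.04 is an SD, as the plan treats it. The point concerns the visit-3 comparison, not the Aim 2 slope. The change should be made because it costs almost nothing, settles the Aim 1 model before the code is broken, and may gain useful power.

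**What to change.** In section 7c, Aim 1, add: *Arms will be compared on visit-3 (post-capsaicin) IENFD in a linear model with treatment arm and visit-1 (pre-drug) IENFD as covariate; the adjusted difference with its 95% CI is the Aim 1 result.* State the significance level and sidedness in the same place.

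Use visit 1 as the baseline. The visit-2 biopsies follow a week of study drug, so treatment could already have affected them. Do not use raw change from baseline, whose variance would be dominated by the baseline SD of 10.1.

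The cost is one sentence and one degree of freedom, with no extra biopsy, visit or participant. If visit-1 and visit-3 densities are uncorrelated, power falls by about 1 point (0.77 to 0.76).

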The study will be done in a blinded manner where the clinical evaluation and the histopathological evaluation of degeneration and regeneration will be done by different teams. Patients will be randomized and given unique patient identifiers by the research coordinators. The staff at the cutaneous nerve laboratory carrying out the histopathological evaluation will not know the identities of the patients or the samples. At the end of the study, the code will be broken and the PI will have access to the histopathological evaluations and patient identities to carry out the statistical analysis.

d. *Justification of why participants will not receive routine care or will have current therapy stopped.*

The patients will continue with their current routine care. They will not be asked to stop any medication or care.

e. *Justification for inclusion of a placebo or non-treatment group.*

Since human nerves degenerate and regenerate at different rates, in order to find out if NR has any therapeutic value, we do need to include a placebo control group.

f. *Definition of treatment failure or participant removal criteria.*

No participant will be removed from the study. Even if the treatment does not lead to faster nerve regeneration, previous research has shown that after topical capsaicin, epidermis fully reinnervates within 6 months. We will examine whether NR can speed this regeneration.

Date: March 25, 2019

Principal Investigator: [name]

Application Number: IRB00210072

- g. *Description of what happens to participants receiving therapy when study ends or if a participant's participation in the study ends prematurely.*

Once the study is completed, the participants will continue with their regular life and medical care. If a participant leaves the study early, the impact on epidermal reinnervation is minimal as it will regenerate.

5. Inclusion/Exclusion Criteria

Study will be conducted in healthy adult patients aged 18-65 without any symptoms, signs or risk factors of peripheral neuropathy.

Inclusion criteria

- Age: 18-65
- BMI<32
- Normal neurological examination defined as NIS \leq 2 (Neuropathy Impairment Score)

Exclusion criteria

- History of peripheral neuropathy
- Any peripheral neuropathy risk factor including diabetes, Vitamin B12 deficiency, HIV-infection, chronic kidney or hepatic disease, hypothyroidism, chemotherapy or other know neurotoxic exposure.
- Pregnancy

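### Aim 2 gives no role to the pre-drug visit-1 biopsy: prespecifying it as a covariate is a cheap, possible gain in precision, and the 30% power figure needs restating

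*Combined protocol and SAP*

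**What the plan says.** Section 7c defines the Aim 2 measure for each subject: "the rate of regrowth is determined by calculating the slope of the line of IEND against time". The planning value is that "this rate of nerve fiber regrowth has been 0.18 ± 0.08 fibers/mm/day". Two power statements follow: "A sample of 20 subjects/group will have a power of 0.8 to detect a 40% or greater change in nerve fiber regeneration" and "We will have a power of 0.6 to detect a 30% improvement in regeneration". Section 7c does not name a test, model, covariate, alpha or sidedness, and it does not list the visits that enter the slope. The slope sentence mentions only the biopsies at two and three months.

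Section 4a sets the order of the biopsies. After screening at visit 1, "the patients will undergo a skin biopsy and be randomized to either the study drug or placebo", and they "will be instructed to take it for a week prior to visit 2". Then, "At visit 2, patients will undergo two baseline skin biopsies", followed by capsaicin. Further biopsies come at visit 3 (patch removal), visit 4 (two months) and visit 5 (three months). The visit-1 biopsy therefore precedes the first dose, while the visit-2 biopsies follow a week of study drug or placebo. Section 7 does not mention the visit-1 biopsy.

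Section 4e justifies the placebo arm with "Since human nerves degenerate and regenerate at different rates". Section 4c has the investigator carry out the analysis after the code is broken.

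**The concern.** The planning SD is 44% of the mean slope (0.08/0.18), and section 4e itself points to differences between people. A pre-randomization measurement that predicts the slope would reduce that variance, and one candidate is already being collected. Because no model is written down, an analyst could adjust for visit 1, for visit 2 or for nothing, and could choose after the code is broken. The choice matters. The visit-2 values are taken after randomization and on drug, so adjusting for them could remove part of a treatment effect. At stake are some power for Aim 2 and a comparison fixed in advance.

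**Working it through.** **Inputs.** From section 7c: 20 per arm, mean slope 0.18, SD 0.08 (the ± is read as an SD), effects of 40% (0.4 × 0.18 = 0.072) and 30% (0.3 × 0.18 = 0.054). Assumed: two-sided alpha 0.05, no dropout, and a correlation r between visit-1 density and slope of 0 to 0.7. The documents give none of these.

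**Step 1: the plan's own figures.** Unadjusted two-sample t-test, 38 df, noncentrality = effect / (0.08 × √(2/20)), critical t = 2.024.
- 40%: 0.072 / 0.0253 = 2.846, power 0.792 (0.812 by normal approximation). Stated 0.8, so it reproduces.
- 30%: 0.054 / 0.0253 = 2.135, power 0.548 (0.569 by normal approximation). Stated 0.6, so it is overstated by about 3 to 5 points.
- One-sided 0.05 gives 0.875 and 0.674 and matches neither.

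The 0.8 is thus recovered from the raw SD with no covariate, which is why the sizing is read as unadjusted.

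**Step 2: visit-1 density as covariate.** Residual SD = 0.08 × √(1 − r²). For a random covariate, chance imbalance multiplies the variance of the arm difference by 1 + 1/(2n − 4) = 1 + 1/36. The test has 37 df and the effect is held fixed. For r = 0.5, for example, the residual SD is 0.0693 and the noncentrality at 40% is 0.072 / (0.0693 × √(0.1 × 37/36)) = 3.24, which gives power 0.884.

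| | Power at 40% | Power at 30% | Effect detectable at 80% power |
|---|---|---|---|
| Unadjusted | 0.792 | 0.548 | 40.4% |
| r = 0 | 0.780 | 0.536 | 41.0% |
| r = 0.3 | 0.817 | 0.575 | 39.1% |
| r = 0.5 | 0.884 | 0.658 | 35.5% |
| r = 0.7 | 0.969 | 0.819 | 29.3% |

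Adjusted and unadjusted power are equal at |r| = 0.17. The cost at r = 0 is 0.792 − 0.780, about 1.2 points.

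**Step 3: is a positive r plausible?** At the mean rate, density at day 90 is 0.25 + 0.18 × 90 = 16.45 fibers/mm. The historical starting density in 7c is 22.7 ± 10.1, and (16.45 − 22.7)/10.1 = −0.62, so under a normal distribution about 27% of people start below that level. If regrowth stops at a person's own starting level (an assumption), those people have flatter slopes, and starting density predicts slope.

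**Step 4: how fragile is the gain?** A simulation of that ceiling drew starting density and rate from the 7c figures, took biopsies at days 0, 60 and 90, fitted a least-squares slope and assumed no biopsy error. Only its differences between adjusted and unadjusted power are used here, for a 40% effect:
- visit-1 value equal to capsaicin-site density: about 12 points gained;
- 50%, 25% or 10% of visit-1 variance reflecting that density: about 4, 2 or 0 points;
- slope from visits 4 and 5 only: about 1 point.

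**The case against.** The strongest reply is that nothing is broken. The 0.8 reproduces, the unadjusted comparison is valid, and leaving out an optional covariate in a 40-subject study is a matter of preference. The benefit rests on an r that the documents do not give and on a visit-1 biopsy site that they do not state. A single punch is also noisy. All of this stands, and it limits the point to an inexpensive improvement of unproven size. What it does not answer is that the between-arm model is unwritten and that the downside is about one point of power.

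Four stronger readings are tempting, and the documents do not support them.
- **That the plan's comparison is biased.** It is not, because randomization protects it.
- **That true Aim 2 power is far below 0.8 because of a regrowth ceiling.** The simulation in step 4 treats 0.18 as an uncapped rate and then caps it. Its placebo slope is about 0.156, not the protocol's 0.18, so its absolute powers are not this trial's powers.
- **That the visit-1 biopsy is the only available covariate.** Age, BMI and visit-1 NAD are also pre-drug, and nothing shows which predicts slope best.
- **That the use of baseline at visit 2 in section 4a makes a stated analysis ambiguous.** It can be read as meaning before capsaicin, and Aim 2 in 7c uses no baseline value. A relabel only prevents later misuse.

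On the 30% figure, rounding may be the cause, since power 0.6 corresponds to a 31.9% change. The figure should still be restated. It is a separate matter that the covariate does not correct.

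**Conclusion.** The point holds as a cheap improvement. Section 7c sizes Aim 2 on the raw slope SD, names no between-arm model and leaves the one pre-drug biopsy unused. Under two-sided 0.05 and 20 per arm, adjusting for it moves power at 40% from 0.79 to between 0.78 (r = 0) and 0.97 (r = 0.7), with r assumed. Equal coefficients of variation for starting density (10.1/22.7 = 44%) and slope (0.08/0.18 = 44%) are compatible with a positive r but do not show one. The realistic gain may be only a few points, depending on how well the visit-1 site matches the capsaicin site and on which visits enter the slope. Confidence is high in the arithmetic and low in the size of the gain. On the same basis that reproduces the 0.8, power for a 30% improvement is about 0.55 (0.57 by normal approximation).

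**What to change.** Before the code is broken, add to section 7c:

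> The Aim 2 comparison is a linear model of each subject's regrowth slope (biopsies at visits 3, 4 and 5) on arm and pre-drug visit-1 IENFD, two-sided 0.05. The visit-2 biopsies are pre-capsaicin, on-treatment values and are not used as the adjustment covariate.

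State where the visit-1 biopsy is taken relative to the capsaicin site. If the two are not comparable, prespecify the unadjusted comparison instead. Relabel the visit-2 biopsies in section 4a to match. Restate power for a 30% improvement as about 0.55, with alpha and sidedness given.

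The cost is a few sentences, with no new visits, biopsies or subjects. The statistical cost is one degree of freedom plus chance imbalance, about 1.2 points of power if r = 0. Aim 1 needs no change on this account.

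### Aim 2's stated power of 0.8 holds only if regrowth stays linear through visit 5, where the 40% effect already brings the average NR participant to normal density

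*Combined protocol and SAP*

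**What the plan says.** Section 7c (Aim 2) defines regrowth as the slope of density on time and reports from earlier work that "this rate of nerve fiber regrowth has been 0.18 ± 0.08 fibers/mm/day". From this it concludes "A sample of 20 subjects/group will have a power of 0.8 to detect a 40% or greater change in nerve fiber regeneration", and adds "We will have a power of 0.6 to detect a 30% improvement in regeneration".

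The Aim 1 part of 7c gives the two ends of the path. In healthy controls "the baseline intraepidermal nerve fiber density was 22.7 ± 10.1 fibers/mm", and after two days of capsaicin "the post-capsaicin IENFD was 0.25 ± 0.04 fibers/mm".

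Under section 4a, participants "will undergo repeat skin biopsies at 2 months (visit 4) and 3" months (visit 5). Section 4f says that after topical capsaicin the "epidermis fully reinnervates within 6 months", and section 8a expects the treated skin to come back to normal or close to it.

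The power statement mentions no plateau. It also does not give the significance level, or say whether the visit 3 value enters the slope.

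**The concern.** A comparison of slopes with a fixed SD assumes that density keeps rising at the same rate up to the last biopsy. Regrowth that ends at normal innervation does not do that in a participant who has already reached normal. The sizing effect puts the average NR participant at that point by visit 5, while the average placebo participant is still well short of it. The visit 5 biopsy would then pull fitted slopes down more in the NR arm than in placebo, so the estimated gain is biased towards zero.

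At stake is how a null Aim 2 is read. Readers would set it against a claimed 80% chance of detecting a 40% acceleration, which the three-month window may not provide.

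**Working it through.** **Inputs, all from 7c unless noted:** n = 20 per group; rate 0.18, SD 0.08 fibers/mm/day; baseline 22.7, SD 10.1; post-capsaicin 0.25; biopsies taken as days 60 and 90 (4a). Assumed: two-sided 5% test, because none is stated.

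**1. Reproduce the stated power.** Power = Φ(Δ / (SD × √(2/n)) − 1.96), with SD × √(2/n) = 0.08 × √0.1 = 0.0253.
- 40%: Δ = 0.4 × 0.18 = 0.072; 0.072/0.0253 = 2.846; Φ(0.886) = 0.81. Exact t: 0.79. The stated 0.8 reproduces.
- 30%: Δ = 0.054; 0.054/0.0253 = 2.135; Φ(0.175) = 0.57. Exact t: 0.55. This is slightly below the stated 0.6.

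**2. Where those rates lead (linear regrowth from 0.25).**
- Placebo, day 90: 0.25 + 0.18 × 90 = 16.45, or 72% of 22.7. It reaches 22.7 on day (22.7 − 0.25)/0.18 = 125.
- NR at +40%, day 90: 0.25 + 0.252 × 90 = 22.93. It reaches 22.7 on day 22.45/0.252 = 89.
- NR at +30%, day 90: 0.25 + 0.234 × 90 = 21.31.
- NR at +40%, day 60: 0.25 + 0.252 × 60 = 15.37.

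**3. Share at own baseline by day 90.** Regrown density minus own baseline has mean 22.93 − 22.7 = 0.23 (NR) or 16.45 − 22.7 = −6.25 (placebo). Its SD depends on the correlation between a person's baseline and rate, which the documents do not give. With rate SD × 90 = 7.2:
- Correlation 0: SD = √(7.2² + 10.1²) = 12.4. NR Φ(0.23/12.4) = 51%; placebo Φ(−6.25/12.4) = 31%.
- Correlation 1: SD = 10.1 − 7.2 = 2.9. NR Φ(0.08) = 53%; placebo Φ(−2.16) = 2%, or about 0% in simulation, where implausibly low densities are floored.

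Skewed (lognormal) baselines and rates raise the NR share to as much as 67%.

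**4. Power under a plateau.** Simulated trials of 20 per arm: density = min(0.25 + rate × day, cap), least-squares slope per person over days 0, 60 and 90, t-test, no biopsy noise, baseline–rate correlation from 0 to 1 unless noted. An additive effect adds 0.072 to every NR rate. A proportional effect multiplies each NR rate by 1.4, so the NR SD becomes 0.112.

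| Model, 40% effect | Power, visits 3–5 |
|---|---|
| No cap, additive | 0.79–0.81 |
| No cap, proportional | about 0.63 |
| Cap at own baseline, additive | 0.42–0.63 |
| Cap at own baseline, proportional | 0.29–0.63 |
| Cap at own baseline, control rates calibrated to an observed 0.18 ± 0.08 | 0.28–0.45 |
| Cap at 120% of own baseline | 0.50–0.71 |
| One common cap at 22.7 | 0.72–0.74 |

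Under most models with a cap at own baseline, the measured gain is about 24–33% instead of 40%. For the 30% effect the same cap gives roughly 0.28–0.50, against the stated 0.6. If the slope used only visits 4 and 5, power for the 40% effect with a cap would be about 0.03–0.20 in the common-SD models.

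**5. Would dropping visit 5 solve it?** Power at the 40% additive effect, slope over visits 3–5 against visits 3–4, with noise as an assumed SD in fibers/mm:
- Cap at own baseline, no noise: 0.42–0.60 v 0.59–0.79.
- Cap at own baseline, noise 5: 0.34–0.45 v 0.35–0.45.
- 20% overshoot, noise 5: 0.41–0.56 v 0.36–0.44.
- No cap, noise 2.5: 0.76 v 0.69. No cap, noise 5: about 0.66 v 0.49.

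The two-month rate gains clearly only with a firm plateau and low noise.

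**The case against.** The strongest reply is that the documents state no cap. The 22.7 ± 10.1 is a population mean with wide spread, so a reader who takes 22.7 as the top of the measurable range infers something the plan does not say. Many people read well above it, and any limit would be each person's own baseline. Section 4f gives no abrupt stop and no plateau at three months, and a linear placebo path reaching 22.7 on day 125 fits full reinnervation within six months. This stands, and it makes the finding conditional.

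Second, the cited 0.18 ± 0.08 is itself a measured slope and may already contain some slowing. That is fair: capping it again lowers the simulated control slope to 0.156 at correlation 0. But calibrating the control arm back to 0.18 ± 0.08 does not restore the power (0.28–0.45).

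Third, the two coefficients of variation nearly coincide (10.1/22.7 = 0.445; 0.08/0.18 = 0.444), which is compatible with regrowth proportional to baseline, though not proof of it. With a proportional gain, NR participants would then reach baseline only at about day 90, and the cap costs almost nothing (0.626 against 0.627 uncapped). This also stands, but power is still below 0.8, because the NR-arm SD grows.

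Fourth, resting the primary slope on visits 3 and 4 alone makes it depend essentially on a single visit 4 biopsy. The noise comparison bears this out, so the documents do not support making that rate the primary measure.

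**Conclusion.** The point holds as a conditional one. The 0.8 is not an arithmetic slip; it follows from the plan's inputs under linear regrowth. That linearity, however, requires about half the NR arm to grow past its own normal density by visit 5, which sits badly with sections 4f and 8a. Every plateau model tested gave power below 0.8 for a slope over visits 3–5: roughly 0.3–0.6 with a hard cap at own baseline, and up to about 0.7 with 20% overshoot.

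No single value in that span can be called the true power. It depends on the baseline–rate correlation, the form of the NR effect, biopsy noise and the visits in the slope, none of which the documents settle. A reader might also infer that a real 40% gain would more likely than not be missed. That is not established either, since the overshoot models sit at or above 0.5.

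**What to change.** In section 7c:

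1. Replace the unconditional 0.8 for a 40% gain, and the 0.6 for 30%, with power that allows for a plateau at about each participant's own baseline. State the range and its assumptions: visits in the slope, baseline–rate correlation, additive or proportional effect, biopsy noise, and test level.
2. Say explicitly that 0.8 applies only if regrowth is linear to 3 months.
3. Keep visit 5, and prespecify the visit 3 to visit 4 rate as a sensitivity analysis. Mean density is expected to be below normal in both arms at day 60 (NR 15.4 fibers/mm under the 40% effect).

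The cost is protocol wording, a re-run power calculation and one more analysis, with no added visit, biopsy or participant. The downside is a less favourable stated power.
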